established. Hence, the aim of this study was to analyze and compare the clinical and radiological results between the two surgical technique, the Tension Band Wiring (TBW) and Hook plate ones, and evaluate the functional outcomes of surgical treatment in displaced, closed, and isolated distal clavicle fractures in adults.

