## **Material and methods**

This study is a comparative retrospective study of 38 patients who had unstable distal clavicle fracture (Neer 2) featured in Figure 1. treated either with TBW technique (Figure 3 and 4) or A.O Hook plate fixation (Figure 2), and presented to the orthopedic department of Tishreen University Hospital, in Lattakia, Syria, between August 30, 2019 and August 30, 2022.

Data was extracted from the medical records of patients in the form of case sheets, discharge cards, x-rays, etc. The type of fracture was determined by Neer's classification.

We included patients who met the following criteria: Patients with unstable distal third clavicle fracture (Neer type 2), aged between 18 and 65 years old. Nevertheless, Patient who had open fractures, pathological fractures, fractures associated with brachial plexus or pulmonary or vascular injury, acromioclavicular joint disruption, and musculoskeletal disease that affects the joint, were excluded.

Preoperative shoulder x-rays in AP with (10-15) ° cephalic tilt (ZANCA View) and axillary view were taken. In addition, Basic lab tests were done for all patients on admission. We used A.O Hook plate with (4-7) holes, (3.5) mm screws and (12.15.18) mm of hook depth, and 2 Kirschner-wires of (2.0) mm and stainless steel wire of (18) gauge in the TBW technique.

Specified postoperative protocol was followed for all patients contained:

1. Arm immobilization with a sling inside the operation room under anesthesia.
2. I.V antibiotics and analgesic
3. A sterile wound dressing was applied routinely.

The surgical stitches were removed after (10-14) days after surgery, and all patients were subjected to the rehabilitation and physical treatment.

One examiner measured the outcome based on Constant-Murley score at 1.5-, 3-, 6-, 9-, and 12- month intervals. In this system, both subjective and objective clinical data are included, with a maximum score of 100 points, as the following: Pain (15 points), activities of daily living (20 points), range of motion of the shoulder (40 points), and muscle power (25 points) were evaluated.

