## Statistical analysis

The Student's t-test, chi-square test with Yates' correction, Fisher's exact test, and Friedman test were used to compare the two groups. The statistic software SPSS 10.0 (SPSS, Inc., Chicago, IL) was used to analyze the data; p values below 0.05 were considered significant.

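### The Friedman test is listed as a comparison of the two techniques, but with independent, unmatched patients no layout of these data makes it a valid between-group test

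*Combined protocol and SAP*

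**What the plan says.** The Statistical analysis section of the combined protocol and SAP names Student's t-test, chi-square with Yates' correction, Fisher's exact test and the Friedman test, and gives all four a single purpose: "Friedman test were used to compare the two groups". It adds that "p values below 0.05 were considered significant". It does not link any test to any outcome.

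The aim, at the end of the Rational section, is to "compare the clinical and radiological results between the two surgical technique". Under Material and methods, the 38 patients were "treated either with TBW technique (Figure 3 and 4) or A.O Hook plate fixation (Figure 2"). No matching, pairing or crossover is described anywhere. The Constant-Murley score, "with a maximum score of 100 points", was measured "at 1.5-, 3-, 6-, 9-, and 12- month intervals". It is the only named score measured repeatedly on each patient.

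**The concern.** Friedman needs blocks of related measurements. Here the related measurements are repeated visits within a patient; the two techniques are in different patients. The stated purpose therefore does not match what the test can do.

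The study exists to compare techniques, and any p below 0.05 is to be called significant. Read as written, a significant Friedman result would count as evidence on TBW versus hook plate when it may show only that patients recovered after surgery. With patients as blocks, a non-significant result would not rule out a constant difference of any size. If change over time was meant, a reader cannot tell that from the text.

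**Working it through.** **Inputs from the documents:** 38 patients, two independent groups, five Constant-Murley visits, maximum 100 points, significance level 0.05. There is no power or effect-size figure to reproduce.

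**Assumptions (not in the documents):** 19 per arm, normal scores with SD 10, AR(1) correlation 0.6 between adjacent visits, 20,000 simulated trials. They set the rates below. They do not affect the algebra.

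There are three ways to lay out the data for Friedman.

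**1. Patients as blocks, techniques as conditions.** Impossible: each patient had one technique.

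**2. Patients as blocks, visits as conditions.** With n = 38, k = 5 and R_j the sum over patients of the within-patient ranks at visit j,

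Q = 12/(nk(k+1)) × ΣR_j² − 3n(k+1) = (12/1140) × ΣR_j² − 684, on 4 degrees of freedom.

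Adding a constant c to all five scores of every patient in one arm changes no within-patient rank, so no R_j and no Q. This needs no assumption beyond the constant shift.

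| Scenario | Friedman rejects |
|---|---|
| Identical arms, 5-point rise over time | 50% |
| Same datasets, 20 points added to one arm | 50% (largest change in Q: 0) |
| Identical arms, 10-point rise | 98% |
| Same datasets, 20 points added to one arm | 98% (largest change in Q: 0) |
| Flat curve, 20-point arm difference | 5.5% |

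In the trials with the 20-point difference, a t-test on each patient's five-visit mean rejects in 100%. Rounding scores and capping them at 100 breaks exact invariance but changes little: with a 20-point difference, 46–51% and 96–98% for the two rises.

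Running Friedman separately in each arm does not help. With identical arms, one is significant and the other is not in 39% of trials (5-point rise) and 34% (10-point rise).

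**3. Visits as blocks, the two group means as conditions.** With five blocks and two conditions, Q = (2s − 5)²/5 on 1 degree of freedom, where s is the number of visits at which TBW has the higher mean.

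- s = 5 or 0: Q = 25/5 = 5, p = 0.025.
- s = 4 or 1: Q = 9/5 = 1.8, p = 0.18.

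The test therefore rejects exactly when all five visits favour the same arm. If the visits were independent, that would happen by chance in 2 × (1/2)⁵ = 6.25% of trials. They are not independent, because the same patients supply every block. With no true difference the rejection rate is 28% under AR(1) 0.6. Under equal correlation of 0.3, 0.6 and 0.8 it is about 21%, 40% and 58%. The test does respond to the arms: under AR(1) 0.6 it rejects in 79% for a 5-point difference and in more than 99% for 10 points. Its fault is false positives, not insensitivity.

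**Check on the replacement.** A t-test on the five-visit mean is a valid between-group comparison, with two limits.

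*Shape of the difference* (19:19, SD 10, AR(1) 0.6):

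| TBW deficit at the five visits | Test on mean rejects | Test at one visit rejects |
|---|---|---|
| 10, 5, 0, 0, 0 | 24% | 85% (first visit) |
| 20, 10, 0, 0, 0 | 70% | 5% (12 months, where the arms are equal) |
| 10, 5, 0, −5, −10 | 5% | 85% (first visit) |

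*Unequal variances* (no true difference, SD 20 in one arm and 10 in the other):

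| Split | Larger SD in | Student's t | Welch |
|---|---|---|---|
| 12:26 | smaller arm | 12% | 5% |
| 8:30 | smaller arm | 18% | 5% |
| 12:26 | larger arm | 1.6% | 5% |
| 8:30 | larger arm | 0.6% | 5% |

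**The case against.** The strongest reply is that this is one loosely worded sentence. Four tests share one verb, the five Constant-Murley visits are a natural place for Friedman, and using it for change within a group is legitimate. The t-test, chi-square and Fisher tests suit independent groups, and no outcome is shown to rest on Friedman. All of this stands, and it limits the point to Friedman's stated purpose. It does not remove the point: nothing in the document gives Friedman another role, and separate within-arm p values would still not compare techniques.

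A second reply is that the invariance holds only for a constant arm difference. That also stands. Material and methods describes restricted motion after TBW until the implant is removed, but typically full motion within three to four weeks after the hook plate, and range of motion carries 40 of the 100 points. Non-parallel curves are plausible, and Friedman over visits can then change. It would still mix any such effect with recovery in both arms and could not attribute it to technique.

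A reader might infer that Friedman can never react to a difference between arms. Layout 3 shows otherwise. A reader might also infer that the plan has no valid between-group analysis, or that the study's conclusions depend on Friedman. The documents support neither.

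**Conclusion.** The point holds in a limited form and should be fixed. As written, Friedman is assigned a between-group comparison that no layout of these data makes valid. Over visits within patients it tests recovery, is unaffected by a constant arm difference, and can be significant from recovery alone. Over group means by visit it reacts to the arms, but with a false-positive rate of about 28% instead of 5% in the base case.

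The mismatch of purpose and the invariance to a constant shift rest on the test's structure and are certain. Every rejection rate is illustrative and depends on the assumed SD, correlation and split, and on equal variances and a constant difference except where these were varied. The documents give no arm sizes or SDs. Whether the authors meant within-group change cannot be settled from the text.

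**What to change.** 1. Remove Friedman from the between-group tests. Alternatively, state that it is used only for change in Constant-Murley over the five visits within a group, and that no TBW versus hook-plate conclusion is drawn from it, including from significance in one arm but not the other.
2. State which test is used for which outcome.
3. Compare Constant-Murley between techniques with an independent-groups test. Use the Welch form of the t-test, because arm sizes and SDs are unknown. Apply it to each patient's five-visit mean or area under the curve, with a stated rule for missed visits, or to one named visit, declared a post hoc choice because the study is retrospective. Report the TBW minus hook-plate difference with its 95% CI.
4. State that the per-patient mean answers only the average-difference question and can miss transient or crossing differences. If curve shape matters, a model with group, visit and group-by-visit terms is an option.

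The cost is a few sentences and a small re-analysis of data already collected, with no new patients or visits. The optional model will be imprecise with 38 patients, and whether SPSS 10.0 can fit it must be checked.

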Furthermore, Radiological assessment was performed immediately after surgery, followed by evaluations at 3, 6, 12, and 24-week intervals to monitor healing progress and implant positioning. Recorded complications included infection, non-union, mal-union, pin migration, hardware impingement, and stiffness. The final outcome was assessed based on union status, time to fracture union, shoulder joint range of motion, ability to perform daily activities, and return to pre-injury status.

In the TBW group: The fixation method involved trans-articular fixation through the acromioclavicular joint, supplemented with an additional cerclage wire tension band for enhanced stability. Following surgery, the operated shoulder was supported with a triangular sling for a period of 4 to 6 weeks. Gentle mobilization was permitted once pain subsided, although full range of motion was limited due to pin impingement until implant removal.

In the Hook plate group: The operative procedure, as outlined in prior studies, involved creating a tunnel in the sub-acromial space posterior to the acromioclavicular joint and inserting the hook into this tunnel. If necessary, the plate was contoured to match the clavicle's shape, with careful consideration given to the appropriate depth of the hook. Dynamic compression was utilized to secure the plate in place. Following surgery, the shoulder was supported with a triangular sling for a period ranging from 2 to 4 weeks. Mobilization commenced at the earliest opportunity, typically resulting in full range of motion within three to four weeks. It is worth mentioning that across both groups, heavy manual labor was prohibited until evidence of solid fracture union was observed.

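### Every p below 0.05 counts as significant, but no primary outcome or visit is named, two different deciding outcomes are described, and the Friedman test is listed for a group comparison it cannot make

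*Combined protocol and SAP*

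**What the plan says.** The aim, at the end of the Rational section, is to "analyze and compare the clinical and radiological results between the two surgical technique" and to evaluate functional outcomes. It does not say which result decides the comparison.

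Material and methods describes a "comparative retrospective study of 38 patients", treated with one technique or the other, who presented "between August 30, 2019 and August 30, 2022". Group sizes are not given. One examiner measured the outcome with the Constant-Murley score "at 1.5-, 3-, 6-, 9-, and 12- month intervals". The score's components include "activities of daily living (20 points), range of motion of the shoulder (40 points").

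The same section continues: "Recorded complications included infection, non-union, mal-union, pin migration, hardware impingement, and stiffness". It then bases the final outcome on union status, time to union, shoulder motion, daily activities and return to pre-injury status. The Constant-Murley score is not in that list.

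Statistical analysis lists Student's t-test, the Yates-corrected chi-square test and Fisher's exact test, and ends the list with "Friedman test were used to compare the two groups". The only decision rule is "p values below 0.05 were considered significant". No test is tied to an outcome or a visit.

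**The concern.** Two problems arise from the same short section.

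First, with one unadjusted threshold and no primary comparison, any outcome or visit that falls below 0.05 may be reported as a difference between the techniques. The document offers two candidates for the deciding outcome, the score and the five-item final outcome, and picks no visit for either. A reader of the results could not tell which comparison was meant to answer the question, nor how many were looked at.

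Second, the Friedman test ranks repeated values within each patient, so group membership does not enter it. It can show change over visits inside one group, but it cannot compare two independent groups. It therefore does not supply a single between-group test of the five score visits, and how those visits are handled stays open.

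Shoulder motion and daily activities also appear twice, as score components and as final-outcome items. Agreement between them and the score could be mistaken for independent confirmation.

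**Working it through.** The plan gives no power or familywise error figure to reproduce.

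**Count of comparisons (Material and methods).** 1 score + 6 complications + 5 final-outcome items = 12. Non-union and union status are the same item, so 12 − 1 = 11. Testing the score at all five visits adds 4: 11 + 4 = 15. Motion and daily activities supply 40 + 20 = 60 of the 100 score points.

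**Assumptions (not in the document).** Two-sided tests; a 19/19 split of the 38 patients; t-tests for score, motion, daily activities and time to union; Fisher tests for the six complications and return to pre-injury status. Event rates, in the order infection, non-union, mal-union, pin migration, impingement, stiffness, return to pre-injury status:
- low: 3, 5, 5, 5, 10, 10, 20%
- base: 5, 10, 10, 10, 20, 20, 30%
- high: 10, 15, 15, 20, 30, 30, 50%

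**Why the simple formula is too high.** With independent tests of exact size 5%, 1 − 0.95^11 = 43.1% and 1 − 0.95^15 = 53.7%. But Fisher's test at 19/19 has a true size of only 0.15% at a 5% event rate, 1.05% at 10%, 2.16% at 20% and 2.38% at 30%.

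**Check by hand, base rates, no correlation.**
- Fisher part: 0.9985 × 0.9895³ × 0.9784² × 0.9762 = 0.904.
- 11 comparisons (four t-tests): 1 − 0.95⁴ × 0.904 = 1 − 0.736 = 0.264. Simulation: 0.265.
- 15 comparisons (eight t-tests): 1 − 0.95⁸ × 0.904 = 1 − 0.600 = 0.400. Simulation: 0.400.

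**Null simulation with correlation, 20,000 trials per setting.** Score visits, motion and daily activities are correlated 0.7 to 0.9, and all other pairs 0 to 0.3. Chance of at least one p below 0.05, 19/19 split, Fisher tests:

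| Comparisons | Low rates | Base rates | High rates |
|---|---|---|---|
| 11 | 0.160–0.191 | 0.205–0.234 | 0.236–0.269 |
| 15 | 0.189–0.252 | 0.232–0.294 | 0.262–0.328 |

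**Sensitivity.**
- Yates chi-square in place of Fisher, base rates: 0.183 to 0.209 for 11, 0.208 to 0.274 for 15.
- Split 25/13, all rates, same correlations: 0.198 to 0.308 for 11, 0.224 to 0.362 for 15.
- Widest setting (25/13, high rates, no correlation, 15 comparisons): 0.459.
- Uniform correlation 0.9, base rates, 19/19: 0.135 for 11, 0.157 for 15.
- Reduced set of 8 (score once; no separate motion or daily-activity test; no pin migration): about 0.13 to 0.20 across the rates.
- Score once plus five complications (no pin migration): about 0.07 to 0.14. By hand at base rates, 1 − 0.95 × 0.9985 × 0.9895² × 0.9784² = 0.111.
- Best of the five score visits alone: 0.15 at correlation 0.7, 0.10 at 0.9.

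**Power, two-sided t-test, 19 per group, 80%.** Detectable difference 0.934 SD at 0.05; 1.265 SD at 0.05/11 = 0.0045; 1.304 SD at 0.05/15 = 0.0033.

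**The case against.** The strongest reply is that the score is already the main outcome, because Material and methods says the outcome was measured with it. That is the closest the text comes to naming a primary. It does not settle the matter: the section then defines a final outcome without the score, and no visit is chosen. Even with the score accepted as primary, picking the best of five visits gives 10% to 15%, not 5%.

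A second reply is that the count is inferred. Complications are only said to be recorded, and the final outcome, in the singular, could be one overall judgement. This stands. The document does not say how many tests are run, so 11 and 15 are conditional counts, and the narrower readings belong beside them.

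A third is that not every low p-value would be false. Material and methods says motion in the wire group was limited by the pins until removal, while the plate group typically reached full motion within three to four weeks. A real early difference in motion or score is plausible, and pin migration is specific to the wire technique. This also stands: the percentages describe the no-difference case only.

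A fourth is that naming a primary now achieves little in a retrospective, non-randomised study. That is partly right. If outcomes had already been seen, or the groups are not comparable, 5% is not assured. Stating which comparison decides, and when it was chosen, still tells the reader how to weigh the result.

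A reader might infer from the dates that the analysis was chosen after outcomes were known: presentations end on 30 August 2022 and ethics approval followed 19 days later, on 18 September 2022. The document does not say when the analysis was chosen or what had been seen by then, so that inference is not supported.

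**Conclusion.** The point holds as a defect of the written rule. One unadjusted threshold covers every test, two deciding outcomes are described and no visit is chosen. Listing Friedman for a comparison of two independent groups is wrong as written, not merely brief.

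The size cannot be fixed from the document, because the group split, event rates, correlations and the number and choice of tests are all unstated. At 19/19 with Fisher tests and the correlations above, it is about 16% to 27% for 11 comparisons and 19% to 33% for 15. The other readings run from about 7% (score once plus five complications, low rates) to about 46% (the widest setting). Every reading examined is above 5%.

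Two stronger statements should be avoided. One is to quote a single narrow range, or the 43% and 54% from independent exact tests, as the study's error rate; each rests on assumptions that the document does not supply. The other is to say that 15 comparisons will be tested, or that any significant early difference would be spurious; the text supports neither.

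**What to change.** Name one primary comparison, for example the Constant-Murley total at one stated visit such as 12 months, tested at 0.05 with the t-test already listed. First confirm that follow-up at that visit is complete enough: no data-extraction date is given, and a patient presenting on 30 August 2022 would not reach 12 months until about the end of August 2023.

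State when the choice was made and whether outcomes had been seen. If they had, label it post hoc and say that 5% is not assured. Add that 5% also assumes comparable groups, since treatment was not randomised.

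Report all other outcomes and visits as secondary or exploratory, with estimates, 95% confidence intervals and no significance claim. Do not present motion and daily activities as evidence independent of the score. State which test goes with which outcome. Remove Friedman from the between-group comparison; keep it, if at all, for change over visits within a group.

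The change is to wording only. The price is that fewer results can be called significant, and with an assumed 19 per group the primary test has 80% power only for a difference of about 0.93 SD. Keeping significance claims for everything under a Holm procedure would need about 1.26 SD at the first step over 11 tests, or 1.30 SD over 15, which is why estimates with intervals are the better choice here.
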